3.3.3 Planned sample size

Phase 1 dose escalation portion

The accelerated 3+3 design applied in Phase 1 does not require sample size specification; the escalation is continued until the MAD (i.e., a dose with an unacceptable number of DLT) is observed. The expansion portion is exploratory; therefore, no statistical sample size justification has been applied.

The dose escalation portion of the study is completed. 26 patients with advanced or recurrent solid tumors and 28 patients with recurrent or progressive GBM or high-grade glioma were dosed. In each of the groups, 24 patients were evaluable for MTD assessment.

Phase 2 dose expansion portion (Simon's two-stage design)

Simon's two-stage design will be used in Phase 2a. The null hypothesis that the true response rate is 14% will be tested against a one-sided alternative. In the first stage, 9 evaluable patients will be accrued. If there are 1 or fewer responses in these 9 patients, the study will be stopped. Otherwise, 10 additional evaluable patients will be accrued for a total of 19. The null hypothesis will be rejected if 6 or more responses are observed in 19 patients. This design yields a type I error rate of 3.7% and power of 81% when the true response rate is 40%.

3.4 Interim analyses

No interim analyses are planned for the phase 1 portion of the study. Upon completion of the phase 1 portion of the study, the Phase 1 data will be cleaned and data will be locked. Advanced or recurrent solid tumors and recurrent or progressive GBM or high-grade glioma will be analyzed separately.

The phase 2a parts will also be analyzed separately once data are cleaned and data locked.

An interim analysis for stage transition in the Phase 2a dose expansion portion will be performed when the specified number of patients required for Stage 1 had at least one post-baseline RANO assessment after having received at least 6 weeks of study treatment, but no later than after the completion of Cycle 12.

If the required number of responses has not been observed at the time of enrollment of the last patient in Stage 1, enrollment may be suspended, or the cohort may be terminated due to apparent futility. If the required number of responses is reached earlier, the interim analysis may be performed earlier, and stage transition may occur based on a joint decision taken by the Investigators and the Sponsor.

4 ANALYSIS POPULATIONS

Separate analyses will be provided for patients with advanced or recurrent solid tumors and for patients with recurrent or progressive GBM or high-grade glioma in the Phase 1 dose escalation portion of the study, and for patients with recurrent GBM in the Phase 2a expansion portion (Simon's two-stage design) of the study.

4.1 All enrolled population

The All Enrolled population includes all patients who enrolled into the study after signing an informed consent form and satisfying inclusion/exclusion criteria.

4.2 Full analysis population (FAP)

The FAP includes all patients who received at least one partial or complete dose of study drug, based on the intent-to-treat (ITT) principle. The FAP will be the primary population for analyzing efficacy in Phase 1.

4.3 Safety population

All patients who receive at least one full or partial dose of BAL101553 and had at least one post-baseline safety assessment must be included in the safety analysis population. In this context, documented information that a patient had no AEs constitutes a safety assessment. The safety analysis population will be used for all safety related analyses (AEs, vital signs, laboratory data, etc.).

For efficacy and safety analyses, patients will be primarily analyzed according to their originally assigned dose group. In the case that intra-patient dose escalation occurs in a substantial number of patients, additional analyses may be produced.

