3.2.5 Dose modifications

3.2.5.1 Dose increases (Phase 1 portion only)

Intra-patient dose increases, including multiple increases, will be allowed to higher dose escalation levels if all of the following conditions apply:

- The patient has completed at least two treatment cycles without experiencing significant drug-related toxicities (i.e., no drug-related AE ≥ CTCAE grade 2) in the most recent cycle.
- The patient has completed the efficacy assessments scheduled at the end of at least each even-numbered cycle and disease progression has not been observed.
- All patients in the higher dosing cohort have completed their first treatment cycle with
 acceptable tolerability and a decision has been taken to start dosing in the subsequent
 dose cohort. The final decision on intra-patient dose increases will be at the discretion
 of the Investigator after review of available safety data for all patients and discussion
 with the Sponsor.

Dose increases will only occur at the start of a subsequent cycle (i.e., Day 1 of the next treatment cycle) for an eligible patient.

Patients receiving increased doses are not considered to be part of the corresponding higher dose cohort for MTD determination, and DLT occurring after a dose increase will not be counted in the formal computation of DLT incidence for any cohort. However, DLT reported after dose increases may be taken into account in dose escalation decisions (Section 3.2.3).

No dose increases are permitted in the Phase2a portion of the study.

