5.5.5 Electrocardiograms

5.5.5.1 Phase 1

ECGs must be performed in accordance with Table 8.

Standard, triplicate, 12-lead ECG must be performed using the pre-programmed device provided by the Sponsor. Measurements should be separated by ~1 min and be taken within a 5 min time window. During PK assessments, ECG recordings must be obtained within the 5 min prior to PK blood sampling. ECG measurements will be made at the following time points:

- Screening: to determine eligibility of patients.
- Day 1 of Cycles 1 and 2: pre-dose; 1 h, 2 h, 4 h, and 8 h after [first] BAL101553 dosing
 For cohorts using a q12h dosing regimen, triplicate ECG will be also be obtained at 14 h (i.e., after the second daily dose) after first dosing on Day 1 of Cycles 1 and 2 (Phase 1).
- Days 8 and 15 of Cycles 1 and 2: pre-dose; 2 h and 4 h after [first] BAL101553 dosing.
- Day 1 of Cycle 3 and all subsequent cycles: pre-dose.
- End of Study visit.
- Triplicate 12-lead ECG should also be obtained when patients experience SBP ≥ 180 mmHg or DBP ≥ 110 mmHg, or whenever clinical cardiovascular signs or symptoms occur.

In patients undergoing intra-patient dose escalation or dose reduction during, triplicate 12-lead ECGs must be obtained on Days 1, 8 and 15 of Cycles 1 and 2, pre-dose and 2 h and 4 h after BAL101553 dosing, at each new dose level. From the third cycle onwards, triplicate 12-lead ECGs will only be obtained pre-dose on Day 1.

ECGs performed at Screening, on Day 1 of Cycles 1 and 2, and any abnormal ECGs, will be transmitted to a central ECG laboratory for evaluation, including QTc assessment.

ECGs must always be recorded after at least 5 min rest and while the patient is in a supine or semi-supine position. ECGs must be assessed by the Investigator or his/her designee. The ECG printouts are to be signed and dated by the Investigator or his/her designee. Further instruction and training on handling the device provided and transmitting data will be provided to the study centers prior to study initiation.

The designated physician at the site must review the ECG to assess any abnormalities including prolongation of QTcF. The pre-programmed ECG device must provide automated QTcF intervals.

For an individual patient, significant prolongation of QTcF will be defined as:

- 1. Increase in the QTcF to > 500 ms, or
- 2. Increase in the QTcF of > 60 ms compared to the respective baseline.

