8.3.2.8 Safety data analysis

The assessment of safety will be conducted in the safety population and will be primarily based on the frequency of AEs and laboratory abnormalities. Other safety data (e.g., electrocardiogram, vital signs, special testing) will be considered as appropriate. Safety data will be presented in individual listings and summary tables. Study drug dose interruptions and study drug dose reductions will be presented in individual listings and summary tables.

Adverse events

AEs and SAEs will be described by body system in individual listings and frequency tables for each dose level and cycle as appropriate.

AEs leading to withdrawal or dose modifications will be presented in individual listings and summary tables.

Laboratory evaluations

Laboratory values will be converted into SI units and the severity grade determined based on CTCAE v5.0 whenever applicable.

The frequency of laboratory abnormalities will be displayed by worst CTCAE v5.0 grade and by dose level and cycle as appropriate. Newly occurring CTCAE v5.0 laboratory abnormalities will be displayed in a separate listing. Shift tables will be provided for laboratory parameters classified according to CTCAE v5.0.

Other safety data

Data from other tests (e.g., electrocardiogram) will be listed. Notable abnormalities will be discussed and shift tables provided as appropriate. Vital signs will be listed and summarized using descriptive summary statistics.

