6.3.3 Adverse events (AEs)

AE tables and listings will display only treatment-emergent AEs. Any non-treatment-emergent AE will be displayed on a separate listing.

Treatment-emergent events are defined as all events occurring after BAL101553 treatment begins, up to 28 days after last study drug administration. Any AE starting prior to first treatment on Cycle 1 Day 1, or more than 28 days after last study drug administration will be considered as non-treatment emergent. The relationship of an AE to treatment is recorded as unrelated, unlikely, possible and probable. For analysis purposes, 'related' AEs will be those reported as possibly related or probably related, or those for which the relationship is unknown.

AEs will be presented in data listings including dose cohort, disease subgroup, patient, dates/times of event, MedDRA SOC, PT, duration of the event, seriousness, CTCAE grade, intensity, drug adjustment, treatment taken, relationship to study drug and outcome.

An overview table (including only treatment-emergent AEs) will be also presented with the number (and percentage) of patients with:

- At least one AE
- At least one related AE
- CTCAE grade 3/4 or severe AEs
- CTCAE grade 3/4 or severe related AEs
- At least one SAE
- At least one related SAE
- AEs leading to dose modifications (i.e. dose reduced or dose interruption)

- Related AEs leading to dose modifications (i.e. dose reduced or dose interruption)
- AEs leading to study drug discontinuation
- Related AEs leading to study drug discontinuation
- AEs leading to death.
- Related AEs leading to death.

The number of events will be also included in this overview table. This table will be displayed by disease subgroup and dose cohort for all the study period.

All treatment-emergent AEs and treatment-emergent AEs related to treatment will be summarized by incidence rate tables broken down by:

- SOC and PT.
- SOC, PT and worst CTCAE grade/intensity.
- SOC, PT and worst CTCAE grade/intensity.
- SOC, PT and drug relationship.

The incidence rate table for treatment-emergent AEs and treatment-emergent AEs related to treatment by SOC, PT and worst CTCAE grade/intensity will be repeated by treatment cycle using the actual dose received within each cycle.

In addition, all treatment-emergent AEs and treatment-emergent AEs related to treatment will be summarized by SOC, PT and

- Worst CTCAE grade and cycle of occurrence of first event.
- Worst CTCAE grade during cycle 1 and during study.

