6.3.4 Laboratory evaluation

Laboratory safety assessments include hematology, biochemistry, cardiac troponin, coagulation and urinalysis.

The laboratory tests for safety analyses consist of the following:

- Hematology: Hemoglobin (Hb), hematocrit (Hct), red blood cell (RBC) count, platelet count and total and differential white blood cell (WBC) count (neutrophil including bands, lymphocyte, monocyte, eosinophil and basophil counts).
- Biochemistry: Serum creatinine, blood urea nitrogen (BUN), uric acid, sodium, potassium, chloride, bicarbonate, magnesium, calcium, inorganic phosphorus, glucose, albumin, total protein, Aspartate amino transferase (AST), Alanine amino transferase (ALT), total bilirubin, alkaline phosphatase (AP), lipase, lactate dehydrogenase(LDH) and creatine phosphokinase (CK).
- Cardiac troponin: Either troponin T or troponin I.
- Coagulation: International normalized ratio (INR) for reporting prothrombin time and activated partial thromboplastin time (APTT).

- Urinalysis: Dipstick analysis for specific gravity, glucose, protein, and blood. Microscopic analysis for white blood cells, RBCs and any additional findings (such as casts).
- Pregnancy test (at screening, D1 of every cycle): Serum or urine test for human chorionic gonadotropin (hCG).

Laboratory values will be converted into SI units and the severity grade determined based on CTCAE v5.0 whenever applicable.

The laboratory parameters will be presented in data listings sorted by disease subgroup, dose cohort, patient, study day, study time and analyte. Out-of-range values will be flagged with h (high) or l (low). Out-of-marked-range values (defined by Basilea SOP LIS-GLO-000412 Preferred Units and Marked Factors) will be flagged with H (marked high) or L (marked low).

Descriptive statistics for each laboratory analyte at each assessment time will be tabulated. The change from baseline will be also summarized.

An analysis of individual patient changes by disease subgroup dose and cohort will be given using shift tables showing the change from CTCAE grade/intensity at baseline to the worst CTCAE grade/intensity (including unscheduled assessments) during the study.

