6.3.6 ECG results

A summary of clinically significant findings from the 12-lead ECG (CRF data) will be provided for each disease subgroup, dose cohort and time point using a shift table. For this analysis, if the findings for the three assessments at Cycle 1 Day 1 pre-dose are different, the baseline will be defined as the worst assessment prior to first dose intake (if Cycle 1 Day 1 assessments are not done, screening assessments will be used as baseline). For each post-dose time point, the worst assessment of the three triplicates will be taken for the analysis.

The 12-lead ECG results (RR interval and QT interval corrected for heart rate (Fridericia correction) (QTcF) interval reported in the CRF) and changes from baseline will be summarized using standard descriptive statistics by disease subgroup, dose cohort and scheduled time point. The mean of the three ECGs measurements taken at each time point will be used for the summary. For this analysis, the baseline value will be defined as the mean of the three ECGs measurements taken prior to first dose intake.

The same analysis will be repeated on central ECG data (Heart rate (HR), RR, PR, QRS, QT, QTcB, QTcF)

ECG results will be presented for each patient in a data listing.

Outlier analysis:

The number and percentage of patients with maximum on-treatment value of QT/QTc intervals, categorized as ≤ 450 msec, >450 msec and ≤ 480 msec, >480 msec and ≤ 500 msec, and >500 msec, as well as maximum on-treatment change from baseline value of QT/QTc intervals, categorized as <5 msec, >5 msec and <10 msec, >10 msec and <20 msec, >20 msec and <30 msec, >30 msec and <60 msec, and >60 msec will be tabulated based on scheduled and unscheduled 12-lead ECG measurements (CRF and central ECG data).

The following abnormalities will also be tabulated:

- PR abnormality: PR increase from baseline $\geq 25\%$ when $PR > 200$ msec
- QRS abnormality: QRS increase from baseline $\geq 25\%$ when $QRS > 100$ msec
- HR abnormality: HR decrease from baseline $\geq 25\%$ when $HR < 50$ bpm, or $\geq 25\%$ increase when $HR > 100$ bpm.

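### Three Phase 1 safety displays (laboratory worst grade, QT/QTc maximum, AE overview) have no pre-escalation or actual-dose version, so findings after a dose increase count under the lower starting dose

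*SAP*

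**What the plan says.** **Grouping rule.** SAP 4.3 states that "patients will be primarily analyzed according to their originally assigned dose group". It then adds: "In the case that intra-patient dose escalation occurs in a substantial number of patients, additional analyses may be produced". No threshold for a substantial number is given, and no method.

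**Dose increases.** Protocol 3.2.5.1 allows one or more increases in Phase 1. The patient must have completed at least two cycles and had no drug-related AE of grade 2 or higher in the latest one. The higher cohort must have tolerated Cycle 1, and the next cohort must have been opened. For the MTD the protocol separates escalated patients: "Patients receiving increased doses are not considered to be part of the corresponding higher dose cohort for MTD determination".

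**Adverse events.** SAP 6.3.3 states that the grade tables by SOC and PT "will be repeated by treatment cycle using the actual dose received within each cycle", and it adds a Cycle 1 versus whole-study table. The AE overview table is shown by disease subgroup and dose cohort over the whole study, with no such split.

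**Laboratory.** The SAP 6.3.4 shift table runs from baseline "to the worst CTCAE grade/intensity (including unscheduled assessments) during the study". Protocol 8.3.2.8 had planned more: "The frequency of laboratory abnormalities will be displayed by worst CTCAE v5.0 grade and by dose level and cycle as appropriate". SAP 6.3.4 contains no by-cycle grade display, and SAP Section 7 declares no change from the protocol.

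**ECG.** SAP 6.3.6 tabulates "The number and percentage of patients with maximum on-treatment value of QT/QTc intervals" and the maximum change from baseline. It names no dose-at-event rule, so the default in SAP 4.3 applies.

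**The concern.** A worst grade or a maximum cannot improve when observations are added. Data collected after an increase can therefore only raise the starting cohort's count or leave it unchanged. A grade 3 sodium or a QTcF above 500 ms first seen at an escalated dose would appear in these tables as a finding at the lower dose.

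These parameters matter here. Grade 3-4 hyponatremia is among the Phase 1 DLTs, and grade 3 QTc prolongation is a listed DLT type (Protocol 3.2.2). Protocol Appendix 3 predicts that 12% of patients at 25 mg/day and 28% at 30 mg/day exceed the exposure at which the modelled risk of hallucinations or grade 3 or higher hyponatremia reaches 50%. A GBM patient who started at 8 mg/day could, under 3.2.5.1, reach higher cleared levels and still be tabulated under 8 mg/day.

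The AE tables do not fully cover the gap. Under Protocol 7.1.1, an abnormal laboratory or test result is an AE only if it causes signs or symptoms, is clinically significant or needs therapy. For other abnormal values, the laboratory and QT tables are the summary by dose.

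**Working it through.** No stated design figure bears on this point. The check counts what enters each cohort's row.

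**1. Cohort sizes (Protocol Appendix 3, Table 22).** Solid tumors: 3+3+3+7+7+3 = 26. GBM/high-grade glioma: 4+3+7+3+8+3 = 28. Both match Protocol 3.3.

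**2. Effect of one patient on a cohort rate.** 1/3 = 33.3 points; 1/4 = 25.0; 1/7 = 14.3; 1/8 = 12.5. The cohort of 8 is GBM at 30 mg/day, directly below the MAD. Its patients had no cleared level to move to, so for escalation alone the practical range is 14.3 to 33.3.

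**3. Scheduled ECG time points after the first dose (Protocol 5.5.5.1 and Table 8).**
- Cycle 1: Day 1, 4 (1, 2, 4, 8 h); Day 8, 3; Day 15, 3.
- Cycle 2: Day 1, 5 (pre-dose plus four); Day 8, 3; Day 15, 3.
- Cycles 1-2 total: 4+3+3+5+3+3 = 21.
- No escalation, through Cycle 4: 21 + 2 pre-dose Day 1 readings = 23.
- Escalation at Cycle 3: at each new dose level "triplicate 12-lead ECGs must be obtained on Days 1, 8 and 15 of Cycles 1 and 2", at three times each. That gives 3 × 3 × 2 = 18, and 21 + 18 = 39.
- The Cycle 3 Day 1 pre-dose reading precedes the new dose, so 18 − 1 = 17 are at the higher dose: 17/39 = 44%.

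**4. Scheduled laboratory draws after the first dose (Table 8, hematology and biochemistry).**
- Cycle 1: Days 8, 15, 22 = 3. Cycle 2: Days 1, 8, 15, 22 = 4. Cycles 3 and 4: Days 1 and 15 each = 4. Total 11.
- The Cycle 3 Day 1 sample is taken before the increase. Cycle 3 Day 15 and Cycle 4 Days 1 and 15 remain: 3/11 = 27%, excluding the End of Study visit.

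**5. Conditional size.** The documents give no count of escalated patients or later events. As an illustration of scale only, grade 3-4 hyponatremia in solid tumors (Table 25) was 0/16 at 2-16 mg/day and 4/10 at 20-30 mg/day, a difference of 40.0 points. Assume k escalated patients from the lower cohorts have a first grade 3-4 value after an increase. The displayed difference is 40.0 − 100k/16:

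| k | Difference (points) |
|---|---|
| 0 | 40.0 |
| 1 | 33.8 |
| 2 | 27.5 |
| 4 | 15.0 |

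**6. Why simple pooling by actual dose is no remedy.** Escalated patients are selected for tolerability. If four event-free escalated patients were merged into the 20-30 mg/day group, its rate would fall from 4/10 = 40.0% to 4/14 = 28.6%. This too is illustrative: the conditions in 3.2.5.1 largely close the route to those two solid-tumor levels.

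**The case against.** The strongest reply is that little depends on these tables. DLT, MAD and MTD use Cycle 1 only, and DLTs after an increase are not counted for any cohort. The MTDs are declared and the Phase 2a dose is fixed. Time-point summaries for Cycles 1-2 precede any increase. Clinically significant abnormalities also enter the AE tables, which have an actual-dose version. The grouping rule is copied from Protocol 8.3.1.2, and the protocol's by-cycle laboratory display was itself only to be given where appropriate. All of this stands. It limits the consequence but does not supply the missing versions.

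A reader might infer more than the documents support:

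- **That the Phase 1 dose-toxicity comparison is flattened.** This needs escalated patients who worsened at the higher dose. With none, the assigned-dose tables are unchanged.
- **That the bias runs one way.** The denser ECG schedule also applies after a dose reduction. A reduced patient's later maximum, at a lower dose, stays in the higher cohort's row and works in the opposite direction.
- **That half of the laboratory data are at the higher dose.** That counts calendar time. By scheduled draws it is about 27%, and the laboratory schedule is not intensified after an increase.
- **That solid-tumor hyponatremia at 20-30 mg/day was misattributed.** The MAD of 30 mg/day cannot meet the condition for an increase, and 20 mg/day had two grade 4 hyponatremia DLTs. The documents show no actual instance.

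**Conclusion.** The point holds for three displays: the laboratory worst-grade shift table, the QT/QTc maximum table and the AE overview table. Under the stated rule, a value or event first seen after an increase is credited to the starting cohort, and no mandatory version of these displays corrects it. The gradient they show can be flattened. Whether it is, and by how much, depends on how many patients escalated and what happened to them, which the documents do not say. The 44% and 27% are shares of scheduled assessments for one hypothetical patient who escalates at Cycle 3 and is followed through Cycle 4; they are not estimates of bias. The conclusion assumes that the QT/QTc table, which names no grouping, follows SAP 4.3. The by-cycle laboratory grade display is also missing from the SAP without explanation. This is a worthwhile, low-cost correction to the reporting, with no bearing on dose determination.

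**What to change.** For Phase 1, in SAP 4.3, 6.3.3 (overview table), 6.3.4 and 6.3.6:

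1. Add a version of each of the three displays by assigned dose, limited to data before the first intra-patient dose increase.
2. Show later values and events in separate rows or columns by the dose being taken at the time. Do not pool them with the higher cohorts. Label data after dose reductions in the same way.
3. Replace the optional provision for additional analyses in SAP 4.3 with this rule, and report the number of escalated patients per cohort.
4. Either add the laboratory worst-grade display by dose level and cycle from Protocol 8.3.2.8 to SAP 6.3.4, or declare its omission in SAP Section 7.
5. Keep the whole-study tables by assigned dose as secondary displays.

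The cost is SAP wording and some extra programming. No new data collection is needed, since the SAP already lists actual dose received. A patient can appear under more than one dose, so columns no longer sum to N; a footnote should say so.
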